At-Home Telehealth Yoga for Treating Chronic Pain in People with Alzheimer's
Disease and Their Caregiver's

Study Protocol and Statistical Analysis Plan

NCT #: 04512040

February 02, 2023

Background

Pain is the most common health complaint in the general population, and within primary care (14). Chronic pain is usually defined as pain persisting for at least 3 months, although many patients suffer pain for years or even decades (15). Chronic pain affects approximately 50% - 78% of veterans (1, 2) with the prevalence of pain increasing with age (12). Chronic pain is the leading cause of work disability globally (16) and costs the US more than \$500 billion each year in lost productivity (17). Chronic pain is treatment-resistant, and pharmaceuticals often bring limited benefit and have significant side effects and risks. The use and abuse of opiates to treat pain has become a major public health issue (18-20). Most chronic pain is musculoskeletal, which is defined as pain from the body's joints, ligaments, muscles, nerves, tendons, and structures that support the limbs, neck, and back (21). In 2012, 54.5% of U.S. adults reported musculoskeletal pain (22). Chronic musculoskeletal pain is even more common in veterans than nonveterans, with a prevalence of 50-75% (2, 23, 24).

Increasing age is the single biggest risk factor for AD (25). AD affects nearly 5% of persons aged >65 years (26) and nearly one third of those aged \geq 85 years (26). AD is characterized by neurodegeneration and is accompanied by a range of cognitive and behavioral problems (27). Like AD, the incidence of chronic pain increases with age (28). Because both chronic pain and AD are strongly linked to age, they are often comorbid, and studies have shown a high prevalence of pain in AD. A recent meta-analysis involving 50,911 AD patients estimated the prevalence of chronic pain in AD to be 46% (3). This figure may be an underestimate because AD patients may be less able to communicate their pain, and request attention less effectively than their cognitively intact peers (29). Both chronic pain and AD are associated with behavioral and psychological problems including depression (30), insomnia (31), cognitive decline (32) and greater functional dependence (32). The co-morbidity of chronic pain in AD can therefore amplify symptoms, leading to poorer outcomes (32, 33). Moreover, recent studies have suggested a biological link between the two conditions such that chronic pain and AD may involve two intertwined pathological processes that can accelerate AD pathogenesis (34).

As life expectancy increases, the increase incidence of AD has become a major concern. The VA has estimated current and future numbers of veterans with dementia (35). The mid-range estimates for the enrolled population for 2019 were 408,933 cases of dementia, and by the year 2029, 465,636 cases dementia (high range estimates for the same time periods were 571,148, and 688,342 cases, respectively). Since AD accounts for ~70% of all dementia cases (36) and chronic pain affects approximately 50% - 75% of veterans (16, 17), it is estimated that 223,277 veterans have co-morbid chronic pain and AD, which will rise to 254,237 by 2029. Since approximately 5.8 million Americans have AD (36) and the prevalence of chronic pain in AD is 55% (3) this translates to about 3.2 million patients in the US general population currently living with both AD and chronic pain.

Nonpharmacological management of chronic pain is high on the list of priorities for both NIH (37) and the VA (38). Cognitive behavior therapy (CBT) is the gold standard behavioral intervention for chronic pain (39). However, effect sizes for CBT for chronic pain are relatively small, with only 43% of CBT trials demonstrating improvements in pain (40). Furthermore, CBT dropout rates are high (41-43). For these reasons, interest is increasing in integrative approaches to health and wellness (44). A recent survey reported CIH techniques are used by ~35% of US adults (45) and CDC data shows that among the movement practices (yoga, tai chi, and qi gong), yoga has increased most over the decade 2002 – 2012 (8), accounting for ~80% of

CIH use. Two key statistics are relevant. First, a recent survey showed rates of participation in CIH practices including yoga were significantly higher among those with a musculoskeletal pain disorder (22) than among persons without such a disorder (41% vs. 24%, respectively). Second, patients with neurological conditions including AD use yoga more frequently than those without neurological conditions (~25% vs. ~17%, respectively) (10). The trend is clear: yoga is increasingly being by AD patients, and more research is needed.

No studies have examined the effects of yoga on chronic musculoskeletal pain in AD. However, multiple reviews have defined the effects of yoga on musculoskeletal pain in other populations. A 2013 meta-analysis of yoga for any type of pain (e.g., back pain, rheumatoid arthritis, migraine/headache) concluded all 16 studies demonstrated positive effects for pain, with an overall moderate effect size (46). In a “review of systematic reviews,” McCall et al. examined thirteen systematic reviews of yoga for treating acute and chronic conditions (47). Chronic pain was one of only three conditions that clearly benefitted from yoga (anxiety and depression also benefitted). Authors concluded that yoga had a consistently positive effect on pain, with a moderate effect size (mean \pm 95% CI) of $0.74 \pm 0.52 - 0.97$ that was slightly lower for fibromyalgia-like pain, ($0.54 \pm 0.11 - 0.96$).

AD patients have many health problems including sleep disorders, functional impairment, depression, and cognitive decline (32). It is reasonable to ask if yoga can treat these problems. Certainly, yoga has shown clear benefits in non-AD populations, including reductions in anxiety (48) depression (49), and improvements in sleep (50). Of particular relevance is the finding that yoga improves cognition in healthy adults, including attention and processing speed, executive function, and memory (51). These findings raise the exciting possibility that yoga could have beneficial effects for cognition in AD patients. A recent review on yoga as an intervention for mild cognitive impairment, or dementia (4) suggests this was the case, especially for attention and verbal memory, and may be mediated by improved sleep and mood. The review concludes that providers should consider yoga as a safe and potentially beneficial health approach for AD.

Caregiver stress is becoming increasingly recognized. Dementia caregiving is associated with increased levels of depression, anxiety, higher use of psychoactive medications; worse physical health and immune function; and an increased mortality rate (52, 53). Thus, yoga treatment for AD patients could also prove useful for their caregivers. Indeed, the suggestion has been made that physical therapeutic recreation programs for dementia patients should be designed to serve both the patient and their caregiver (6). By performing therapy yoga could help reduce caregiver depression and anxiety and help guide and motivate AD patients to practice during non-class days.

Interventions such as yoga pose greater demands on time and travel than many conventional medical treatments, making it especially difficult for individuals who have AD, chronic pain and/or live in remote areas. As part of a VA initiative to investigate the geographic, clinical, and social barriers to accessing in-person care, detailed information was collected on barriers to accessing healthcare from 1,295 veterans (unpublished data) (54). Results show that barriers included travel time and costs, health conditions, and bad weather. As a result, many individuals may not be able to attend in-person yoga classes. Possible behavioral and social problems in AD may discourage the caregiver from bringing AD patients to group classes, thus compounding problems of access.

Home-based yoga is a very attractive solution to address problem of access. The successful implementation of teleyoga could advance and elevate the treatment of AD and

caregivers. To date, only two small studies have examined the feasibility of at-home teleyoga involving patients with COPD (55) or cancer (56). Both studies reported negative experiences with the technology, and both concluded that internet-based yoga could be feasible if the technology was simplified.

Objectives

Specific Aims and Hypothesis

Specific Aims:

1. Modify an existing teleyoga intervention to use with AD patients and their caregivers and address the technical challenges of at-home teleyoga.
2. Demonstrate the feasibility of conducting group teleyoga with AD patients and their caregivers.

Hypothesis 1 (primary): It will be feasible to maintain an a priori adherence to $\geq 75\%$ classes.

Hypothesis 2 (secondary): Treatment satisfaction as measured by the Multi-Dimensional Treatment Satisfaction Measure will be neutral or positive for all factors.

Study Design

No randomization into treatment groups will be needed in this study. The study involves the development of the technical methods and yoga protocol design needed to deliver at-home yoga instruction via videoconferencing.

Recruitment: 15 dyads (pairs of Alzheimer's disease patients and their caregivers) with chronic musculoskeletal pain will be recruited through different streams such as flyers posted at Stanford Alzheimer's Disease Research Center, and VAPAHCS Pain Clinic. We may also ask VA providers to refer their patients with chronic pain, contacting organization that provide guidance and support for people with Alzheimer's disease or chronic pain, web-based advertising, local advertising, social media advertising (Facebook, Twitter and Instagram using Web Based Recruitment Text, and mass-mailings to potential participants who may meet study eligibility criteria. To recruit AD patients, we may also use Brain Health Registry, which is a web-based platform run by UCSF to match patients with AD with suitable clinical trials (<https://www.brainhealthregistry.org/for-investigators>). The BHR will send our study information to interested prospective participants. These materials are attached to Tab 16 and include a BHR study description, BHR initial email invitation, BHR first follow-up email, and BHR second follow-up email.

Individual sessions: Yoga will be first be provided individually. That is, yoga sessions will include the yoga therapist, one AD patient and one caregiver. We will recruit n=5 dyads (5 AD patients, 5 caregivers).

Group sessions: The study will also demonstrate the feasibility of providing group yoga. Feasibility will be measured for recruitment, retention, and adherence. We will recruit n=10 dyads (10 AD patients, 10 caregivers). When the required number of participants have been identified, the study team will schedule baseline assessments. After the baseline assessment, the cohort will receive group yoga. We currently estimate that due to technical limitations of

instructing yoga via videoconferencing, the largest group size will be 10 participants. Since this is a feasibility study, the study is not powered for efficacy.

Yoga Intervention: We will adapt the yoga protocol from the active award. The protocol is 12 weeks in duration, 1 class/week, class length of 75 minutes, with additional homework 15-20 mins on 5 non-class days/week. The protocol uses seated/standing/supine yoga postures, breathing, and meditation, and contains standard modifications in cases of limited mobility. Participants will also receive a homework manual describing simple and safe exercises to practice for homework.

The sample size (n=15) is small, but will provide the necessary information on recruitment, adherence, acceptability and self-report measures of pain and pain-related function to plan a larger fully powered efficacy study in the future. Developing a yoga intervention for groups is typical of yoga interventions, as it allows a small staff to treat many individuals simultaneously.

The main purpose of this study is to collect information on various aspects of feasibility and not efficacy of treatment, therefore we contend that a priori matching or a priori stratification is not relevant in this case. We have also considered another challenging feature of the design; caregivers and AD patients will interact. Participants may also interact with one another directly in their groups. This interaction creates the expectation that some level of intraclass correlation (ICC) will develop such that AD patient and caregiver responses to treatment will be positively correlated. The magnitude of the ICC depends on the type, duration, and intensity of these interactions, and are currently unknown. That ICC may be negligible at baseline, but it can develop over the course of the trial. We contend that with a limited number of treatment cohorts (2), and the limited number of yoga teachers (1-2) we have very limited ability to estimate the ICC, or the component of variance associated with the group or yoga teacher. Again, the main purpose of this study is to collect information on various aspects of feasibility and ICC is of negligible importance in our design, and a priori matching or a priori stratification is not necessary in this case.

Month											
1	2	3	4	5	6	7	8	9	10	11	12
Recruit AD & Caregiver (n=5 pairs)			Treat AD & Caregivers one-on-one format			Treat AD & Caregivers group format			Data analysis, manuscript submission and funding application		
			Run AD & Caregiver pairs (n=10 pairs)								

Table 1. Recruitment Table

Statistical Plan and Data Analysis

The main analytic strategy will be descriptive statistics for pre- and post-intervention assessments for AD patients and their caregivers. For feasibility of retention and adherence, we aim to reach at least 65% retention. For feasibility of treatment fidelity, we will aim for $\geq 95\%$ of treatment components. For the outcomes that will be measured repeatedly (i.e., both at baseline

and post-treatment), we will estimate how they change over time (pre to post). Note that some of the assessment measures used are used only for AD patients or caregivers. The results will be reported for both groups separately. Accordingly, in terms of AD patient outcomes, we will estimate changes in pain (DVPRS), depression (BDI-II), sleep (PSQI) and cognition (CanTab). These results will provide preliminary data on target engagement and therefore will inform and shape the future trial in terms of elucidating the mechanism of action. For the caregiver measures, we will estimate changes in caregiver burden (Revised Memory and Behavior Problems Checklist), quality of life (SF-36), depression (BDI-II), and sleep (PSQI). We will also explore the relationship between changes in patient outcomes and their caregiver outcomes. For all analyses regarding changes in outcomes, we will first employ simple paired t-test (pre vs. post) given the correlation between pre and post measures. We will also estimate changes based on longitudinal mixed effects modeling using maximum likelihood estimation. We will put in rigorous effort to minimize missing data. Nonetheless, we expect some attrition by post intervention assessment. In our mixed effects modeling, data points that are missing due to attrition or missing assessment will be handled assuming that data are missing at random conditional on observed information. In all statistical analyses, we will focus on collecting preliminary data on clinical significance (i.e., effect size) instead of making formal inference (i.e., p-value).

Inclusion/Exclusion Criteria

Inclusion Criteria for AD patients (As determined by):

- Diagnosis of probable Alzheimer's disease- Baseline
- Mini-Mental State Examination (MMSE) score 18-25 (Mild AD) (screening interview) \geq 18 years old
- Has a primary care provider who can provide medical clearance for participation in the study
- Diagnosis of chronic musculoskeletal pain $>$ 6 months
- Minimum pain intensity at screening visit: pain rated \geq 4 on a 0-10 Numeric Rating Scale (NRS)
- Not begun new pain treatments or medications in the past month
- If on a psychotropic medication regimen: stable regimen for at least 4 weeks prior to entry to the study; willingness to remain on a stable regimen during the 12-week acute treatment phase
- English literacy
- Wireless internet connection at home (Screening interview)
- Has a caregiver who is willing to accompany AD patient for treatment, and who can receive yoga treatment at the same time as AD patient.

Exclusion Criteria for AD patients (As determined by):

- Participation in another concurrent clinical trial
- Back surgery within the last 12 months

- Back pain potentially attributed to a specific underlying cause, disease, or condition (VA EMR; screening interview)
- Baseline pain <4 or ≥9 on a 0-10 Numeric Rating Scale (NRS)

Inclusion Criteria for CAREGIVERS of AD patients (As determined by):

- Are caring for a patient diagnosed with AD who will practice yoga together with them
- Has a primary care provider who can provide medical clearance for participation in the study (Yoga Medical Clearance Form)
- Exclusion Criteria for Caregiver
- Participation in another concurrent clinical trial
- Attended or practiced yoga ≥ 1 x in the past 12 months
- Attended or practiced yoga ≥ 1 x in the past 12 months

Informed Consent Process

Participants will be recruited from four sources: Brain Health Registry, the VAPAHCS Pain Clinic, local advertising, and web-based advertising. These sources will result in either 1) the potential participant calling the study team or 2) with the participant's consent, the study staff contacting them directly. Study candidates will be invited to VAPAHCS for a screening visit, during which the Project Manager will obtain informed consent and review the Health Insurance Portability & Accountability Act (HIPAA) document.

The informed consent process will involve the AD patient and their caregiver together. They will complete separate consent forms. As we are enrolling AD patients with impaired consent capacity, the caregiver will act as a legal authorized representative (LAR) and provide consent for the AD patient, who will be asked to provide their assent. These forms will include the HIPAA document and are estimated to take about 60-90 minutes. It will take place in a quiet office or interview room, located in the same building as the PI, who will be available to answer any of the study candidate's questions.

1. The Project Manager will explain the information contained in the written informed consent forms (purpose, procedures, risks, benefits, alternatives to participation, etc.) and HIPAA documents to the study candidates verbally, in lay language.
 - a. The Project Manager will check for comprehension, allow the study candidates ample opportunity to ask questions throughout the process, and repeat the information, as necessary.
 - b. Care will be taken to inform the study candidate that their participation is entirely voluntary, and they may withdraw at any time and for any reason without penalty or loss of benefits to which they would otherwise be entitled.
 - c. Study candidates will then be asked to carefully read the informed consent form to consider whether or not to participate in the research and to ask questions.

- d. To ensure that the study candidate understands the research, they will next be asked to summarize the consent form and HIPAA addendum, with a special focus on the discomforts, risks, benefits, and confidentiality sections.
2. If the study candidate demonstrates (by stating in his/her own words) an understanding of the purpose, risks, and benefits of the study and agrees to participate in the study, he/she will be asked to initial each page, in addition to sign and date the last page of the consent form and the HIPAA document.
3. The Project Manager who oriented and obtained informed consent will sign and date the informed consent form.
4. The Project Manager will provide each enrolled participant with a photocopy of the original signed copy and keep the original signed copy in a binder in a locked cabinet.

The emphasis on the voluntary nature of participation is designed to minimize the possibility of coercion or undue influence on participation. The study candidate will be given time to understand the written informed consent form and make an informed decision. All treatments for this study will be provided in group formats, so potential participants will be reminded that full anonymity cannot be maintained. Following the informed consent process, the enrolled participant will complete other measures (See Research Strategy).

Screening Procedures

Potential participants (n=15) will be screened via phone. The Project Manager will obtain informed consent and review the Health Insurance Portability & Accountability Act (HIPAA) document. After obtaining informed consent, a trained researcher will collect demographic information (Demographic Questionnaire). Screening for protocol eligibility for AD participants will include the MMSE, PEG, DVPRS and Clinical DVPRS.

Study Assessments

Demographics Questionnaire: Documents age, gender, education, and race/ethnicity.

Clinical Questionnaire: Self-report document focusing on the existence of 78 health symptoms taken from a list of ICD-9 codes that are highly likely to represent chronic pain.

Medication Use: Self-report of all current pharmacological and non-pharmacological treatments.

Yoga Home Practice Log: Log for participant to document their yoga home practice on non-treatment days.

BDI-II Beck Depression Inventory-II (BDI-II): Contains 21 self-report questions, scored on a 0-3 scale, related over the past two weeks to sleep, appetite, punishment, suicide, and interest in sex.

Brief Pain Inventory-Short Form (BPI-SF): Assesses intensity and impact of pain on functioning on a 0-10 rating scale. Interference is assessed on daily life (general, walking, work, mood, enjoyment, relationships, sleep). The BPI is recommended by the Initiative on Methods, Measurement, and Pain Assessment in Clinical Trials (IMMPACT) group for inclusion in clinical trials evaluating pain.

Defense and Veterans Pain Rating Scale (DVPRS): A five-item scale: one 0-10 pain intensity numeric rating scale and four supplemental items measuring functional outcomes (general activity, sleep, mood, level of stress). The pain intensity scale is designed to improve upon

existing scales by using visual cues and word descriptors to anchor pain ratings with perceptual experiences and limitations imposed by pain.

PEG: A 3-item pain measure derived from the Brief Pain Inventory and validated in ambulatory care settings. It includes 1 severity item (average pain) and 2 interference items (enjoyment of life and general activity).

Pittsburg Sleep Quality Index (PSQI) (62): Contains 10 self-report questions regarding sleep habits over the past month, including discrete responses (e.g. amount of sleep) and responses scored on a 0-3 scale (“not during the past month” to “three or more times per week”), related to sleep quality, medication use, motivation, and fatigue. A global sum score indicates level of sleep difficulties.

Treatment Satisfaction: Assessed using the Multi-Dimensional Treatment Satisfaction Measure (MDTSM). The measure consists of 11 subscales assessing treatment process and outcome attributes. Each subscale has 1-8 items (see Table 5). Each question except the Discomfort subscale is rated on a five-point scale ranging from “not at all (0)” to “very much (4)”. Thus, a score of 2 represents a rating of neutral satisfaction. The instrument was developed for behavioral interventions and is designed to provide a comprehensive set of treatment attributes to consider when evaluating treatments in the context of pilot studies. It is designed to be completed after exposure to an intervention, to point to aspects of treatments that are viewed favorably or unfavorably. The MDTSM is relevant to many types of behavioral interventions and can be tailored to our yoga intervention. The MDTSM subscales demonstrates good internal consistency, reliability, and validity.

Treatment Fidelity: Of the 12 sessions recorded, we will randomly select a session from weeks 1-4, weeks 5-8, and weeks 9-12 for a yoga instructor to review. Following standard procedures (64), they will review the sessions using a manual checklist for instructor adherence to the yoga manuals, which will consist of a Yes/No prompt for each procedure or instruction. We will set a benchmark for minimum competency at $\geq 95\%$ of treatment components (64).

Cambridge Neuropsychological Test Automated Battery (CANTAB): Cognitive function was measured with the Cambridge Neuropsychological Test Automated Battery (CANTAB) at baseline and end of treatment. Three tests were administered (PAL, SWM and RVP).

Revised Memory and Behavior Problems Checklist (RMBPC) (68): Assesses behavior problems in dementia patients. Contains 24 caregiver-report questions, scored on two scales; whether the behavior was observed (“yes”/“no”), and the degree it affected the caregiver. Scales yield scores; one total score for patient problems and three subscale scores (memory-related, depression, and disruptive behaviors), and parallel scores for caregiver reaction.

SF-36: Health related quality of life-short form (69). Eight scales measuring physical functioning, role limitations due to physical problems, bodily pain, general health perceptions, vitality, social functioning, role limitations due to emotional problems, and mental health.

	Data Collection			
	Screening	Baseline	Yoga (wks 1-12)	Post-treatment
Background				
Consent Form	×			
Demographic Questionnaire	×			
Clinical Questionnaire	×			
Yoga Medical Clearance Form	×			

Medical Use		x		x
Yoga Home Practice Log			x	
Mental Health				
BDI-II		x		x
Pain/QOL/Physical				
BPI-SF		x		x
DVPRS	x			
PEG	x	x		x
PROMIS-PI		x		x
Behavioral				
Treatment Satisfaction				x
Provider Suggestions				x
Patient Safety			x	x
Treatment Fidelity			x	

Table 2. Study Measures and Timetable of Data Collection

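### Uncontrolled pre-post changes in 10 to 15 patients are described as target-engagement and mechanism data, which a design without a comparator cannot supply

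*Combined protocol and SAP*

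**What the plan says.** The study is single-arm: "No randomization into treatment groups will be needed in this study" (Study Design). It plans 15 patient-caregiver dyads, 5 treated individually and 10 in the group phase ("We will recruit n=10 dyads (10 AD patients, 10 caregivers"). The retention goal is stated as "we aim to reach at least 65% retention".

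The Statistical Plan and Data Analysis section estimates pre-to-post change in the patients' pain (DVPRS), depression (BDI-II), sleep (PSQI) and cognition (CANTAB), by paired t-test and then a mixed model. It adds: "These results will provide preliminary data on target engagement and therefore will inform and shape the future trial", and the same sentence goes on to mention mechanism of action. On inference it says: "we will focus on collecting preliminary data on clinical significance (i.e., effect size) instead of making formal inference (i.e., p-value". No confidence interval is mentioned. Study Design adds: "The sample size (n=15) is small, but will provide the necessary information on recruitment, adherence, acceptability and self-report measures of pain", with the purpose of planning a fully powered efficacy trial.

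Patients are selected on pain twice. The inclusion criteria set a floor of 4 on a 0-10 scale ("Minimum pain intensity at screening visit: pain rated"). The exclusion criteria remove "Baseline pain <4 or ≥9 on a 0-10 Numeric Rating Scale (NRS".

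**The concern.** A change within one group is the sum of any yoga effect and everything else that moves the score over 12 weeks. For all four outcomes that includes natural course and the attention of a weekly class. For CANTAB it includes familiarity with the tests. For pain it includes regression to the mean, because patients enter only when their rating lies inside a window. Nothing in the plan names these as limits on what the changes can show.

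Putting effect size in place of the p-value does not help. An effect size carries the same bias as the change it is computed from, and it is not the same thing as clinical significance. At stake is a reader, or the team planning the next trial, taking a pre-post effect from a handful of patients as evidence that yoga acted on its target.

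**Working it through.** The documents contain no power, sample-size or effect-size calculation for this study, so there is no stated figure to reproduce.

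**Number of patients.** 5 + 10 = 15 planned; 0.65 × 15 = 9.75, or about 10 with post-treatment data if retention just meets its goal. So n = 10 to 15.

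**Regression to the mean for pain.** From the documents: rating at least 4 at screening, and 4 to below 9 at baseline. Assumed, because the documents do not give them: source mean μ 3 to 6, SD σ = 2, and correlation r 0.6 to 0.8 between any two occasions, with normal ratings.

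If one value restricted to 4 to <9 is the pre value X, the expected fall with no treatment effect is (1 − r) × (E[X | 4 ≤ X < 9] − μ). The SD of change is σ × √[(1 − r)²v + 1 − r²], where v is the variance of the truncated standardised rating.

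Example, μ = 3 and r = 0.6:
- standardised limits (4 − 3)/2 = 0.5 and (9 − 3)/2 = 3
- truncated mean (0.3521 − 0.0044)/0.3072 = 1.13 SD, so E[X] = 3 + 2 × 1.13 = 5.26
- fall 0.4 × 2.26 = 0.91 points
- v = 0.249, so SD of change = 2 × √(0.16 × 0.249 + 0.64) = 1.65
- standardised fall 0.91/1.65 = 0.55

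With both cuts applied (screening ≥ 4 and baseline 4 to <9, change measured from baseline), the same quantity was obtained by simulation. Expected fall in SD of change:

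| Source mean | One value, r = 0.6 | One value, r = 0.8 | Both cuts, r = 0.6 | Both cuts, r = 0.8 |
|---|---|---|---|---|
| 3 | 0.55 | 0.37 | 0.38 | 0.23 |
| 4 | 0.37 | 0.25 | 0.26 | 0.15 |
| 5 | 0.21 | 0.15 | 0.14 | 0.08 |
| 6 | 0.07 | 0.05 | 0.03 | 0.01 |

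The first case therefore spans about 0.05 to 0.55 and the second about 0.01 to 0.38. Widening the one-value case to SD 2 to 2.5 and r 0.5 to 0.9 gives 0.03 to 0.63.

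**Which case applies.** The documents do not settle this. The cuts are on a numeric rating scale, and the named pain outcome is DVPRS, which contains a 0-10 item and is also a screening measure (Screening Procedures). Table 2, as it reads here, marks DVPRS at screening only. If that screening value is both the eligibility rating and the pre value, it is restricted directly. BPI-SF is marked at baseline and post-treatment.

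**Precision.** This step needs no outside input. For an observed paired d of 0.5, t = 0.5√n, and the limits come from the noncentral t distribution divided by √n.
- n = 10: t = 1.58 on 9 df; noncentrality limits −0.545 and 3.631; divided by 3.162, the 95% CI is −0.17 to 1.15.
- n = 15: t = 1.94 on 14 df; limits −0.179 and 3.991; divided by 3.873, the 95% CI is −0.05 to 1.03.

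The half-width for a mean change is 2.262/3.162 = 0.72 SD of change at n = 10 and 2.145/3.873 = 0.55 at n = 15.

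**The case against.** The plan disclaims a good deal. It calls itself a feasibility study, says it is not powered for efficacy, makes descriptive statistics the main strategy and sets formal inference aside. Both hypotheses, on adherence and on treatment satisfaction, are untouched. That stands, and it limits the seriousness of the point. It does not withdraw the sentence on target engagement and mechanism, because giving up power and p-values does not give up a causal reading.

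Three stronger readings might be inferred, and the documents do not support them.

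- *Regression to the mean alone produces a small-to-moderate effect.* That depends on inputs the plan does not give. Patients need diagnosed musculoskeletal pain of more than 6 months and come partly from a pain clinic, so a source mean near 6 is plausible, and there the effect is at most 0.07 SD of change under the SD 2 assumptions. Nor are patients simply selected for high pain: ratings of 9 and above are excluded, which reduces the fall.
- *All four outcomes are biased in this way.* Only pain is restricted on its own value. The MMSE range of 18 to 25 could touch cognition indirectly. The lack of a comparator does affect all four.
- *The next trial will be too small.* No passage says that the observed effect will be its assumed effect. Pain data could inform planning through SDs or choice of instrument. The wording leaves that use open but does not state it.

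**Conclusion.** The target-engagement and mechanism claim is wrong as written: a single-arm change in 10 to 15 patients cannot show either. This rests on the design alone and needs no assumption. For pain, regression to the mean adds a possible bias in favour of yoga of about 0.05 to 0.55 SD of change (one restricted value) or 0.01 to 0.38 (both cuts), conditional on the assumed mean, SD and correlations. It should be described as ranging from nil to moderate, not as a known quantity. The intervals around d = 0.5 run from slightly below zero to above 1, too wide for the estimate to serve as a planning effect even without bias. The change should be made, but the feasibility aims do not depend on it.

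**What to change.** 1. Report each change in raw units with a 95% CI, the baseline SD, the SD of change and the pre-post correlation.
2. Replace the target-engagement and mechanism sentence with a statement that the changes are uncontrolled, are not attributable to yoga, and will not be the assumed effect in the next trial, which will take SD, pre-post correlation, retention and adherence from this study.
3. Leave eligibility unchanged. State which pain value is the pre value, reconcile this with the DVPRS row of Table 2, use a pre-treatment value separate from the eligibility rating where one is already scheduled (baseline BPI-SF), and name regression to the mean as a limit. PEG is less suitable because it is also a screening measure.

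Item 3 may reduce regression to the mean without removing it. With selection on screening alone and a separate baseline, it is zero if correlations are equal over time, but 0.05 to 0.23 population SD if the screening-to-post correlation is 0.2 below the screening-to-baseline one. The baseline exclusion also still applies.

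The cost is SAP wording and routine output, with no new data collection for the BPI-SF option. The downside is a weaker headline claim.
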